11.4	Glossary of Abbreviations.....	106
11.5	Protocol Amendment 1 Summary	108
11.6	Protocol Amendment 2 Summary	111
11.7	Protocol Amendment 3 Summary	113
11.8	Protocol Amendment 4 Summary	115
11.9	Protocol Amendment 5 Summary	118

11.10 Protocol Amendment 6 Summary	126
--	-----

List of Tables

Table 1	Dosage/Dose Regimen – Stage 1 Dose Escalation in Patients With Moderate to Severe Dry Eye Disease.....	12
Table 2	Dosage/Dose Regimen – Stage 2: Baseline Dose and Retreatment in Patients With Moderate to Severe Dry Eye Disease	13
Table 3	SCHEDULE OF VISITS AND PROCEDURES: Stage 1.....	20
Table 4	SCHEDULE OF VISITS AND PROCEDURES: Stage 2.....	22
Table 5	Investigator Procedure Assignments.....	24
Table 6	Stage 2: Randomization/Stratification Groups	41
Table 7	Baseline Treatment and Retreatment Regions	44

List of Figures

Figure 1	Stage 1 Study Flow – Dose Escalation in Patients With Moderate to Severe Dry Eye Disease.....	14
Figure 2	Stage 2 Study Flow – Baseline Dose and Retreatment in Patients With Moderate to Severe Dry Eye Disease	15

Structure:

Stage 1: multicenter, randomized, investigator-masked, dose escalation, vehicle-controlled

- single-dose, paired-eye comparison
- paired-eye comparison, retreatment at week 12 (cohorts 6C and 6D)

Stage 2: multicenter, randomized, investigator-masked, parallel treatment groups, vehicle-controlled

- single dose, bilateral treatment at baseline
- bilateral retreatment at week 12

Duration:

Stage 1: The duration per patient will be approximately 26 weeks (from screening to week 24 visit).

Stage 2: The duration per patient will be approximately 26 weeks (from screening to week 24 visit).

Study Treatment Groups:

Stage 1: Vehicle, F1 [redacted] and F2 [redacted]

Baseline and retreatment cohort 6C and 6D: F1 [redacted] and F2 [redacted]

Stage 2: Baseline and retreatment groups: up to 3 dose groups: vehicle, CFI [redacted], and CFI [redacted]

Controls:

Stage 1: sham [redacted] treatment, vehicle

Stage 2: vehicle

Dosage/Dose Regimen:

Stage 1 will sequentially examine the safety of doses [redacted] of F1 and F2 administered [redacted]

[redacted]

[redacted]

[redacted]

[redacted]

[redacted]

[redacted]

[redacted]

[redacted]

[redacted]

[redacted]

[redacted]

[figure not shown]
[redacted]

[redacted]

[redacted]y,

Approval Date: 19-Jan-2017

[Redacted text block]

Approval Date: 19-Jan-2017

Dosing in stage 2 will begin as a bilateral-eye treatment of CFI or vehicle. In the absence of significant safety findings (determined by the investigator) at 12 weeks, patients in treatment group 1 will be retreated with vehicle in both eyes and followed for another 12 weeks. In the absence of significant safety findings (determined by the investigator) at 12 weeks, patients in treatment groups 2 and 3 will be retreated with CFI in both eyes and followed for another 12 weeks. The dose and dose regimen for stage 2 are provided in Table 2.

[figure not shown]
Randomization/Stratification:

Stage 1: Within each cohort, patients will be randomly assigned with respect to the eye, right or left, to receive F1 or F2 (or vehicle for cohort 1). The contralateral eye will receive vehicle [redacted]

[figure not shown]
Stage 2: Patients will be allocated in a randomized fashion to the treatment groups. This randomization will be stratified by Sjögren's syndrome (presence or absence) at screening.

Approval Date: 19-Jan-2017

Approval Date: 19-Jan-2017

Approval Date: 19-Jan-2017

Study Population Characteristics

Number of Patients:

Up to 87 patients will be enrolled.

Stage 1: Stage 1 will have up to 63 patients and approximately 10 cohorts (cohorts 1 to 6D). The anticipated numbers of patients per cohort are 3 for cohort 1, 4 for cohorts 2, 6C, and 6D, and 8 each for cohorts 3 through 6B.

[Redacted]

Condition/Disease:

Stage 1: patients with moderate to severe dry eye disease

Stage 2: patients with moderate to severe dry eye disease

Key Inclusion Criteria:

Stages 1 and 2:

- male or female, at least 18 years of age at screening visit (week -2)
- at baseline visit (day 1), dry eye disease (keratoconjunctivitis sicca) in both eyes, characterized by the following clinical signs:

d [Redacted]

[Redacted]

- a [Redacted]

Key Exclusion Criteria:

Stages 1 and 2:

- use of topical RESTASIS or any other topical ophthalmic preparation of Cyclosporine (CsA) within 3 months prior to the baseline visit (day 1) and unwilling/unable to discontinue use for 3 months prior to baseline, or anticipated use during the study
- any use of systemic or dermatologic CsA or other calcineurin inhibitors within the 3 months prior to the screening visit (week -2), or anticipated use during the study
- topical ophthalmic use of anti-inflammatory medications (nonsteroidal anti-inflammatory drugs [NSAIDs] or glucocorticoids) within 1 month prior to the screening visit (week -2), or anticipated use during the study
- [Redacted]
- any use of topical ocular medication other than artificial tears within 1 month prior to the screening visit (week -2), or anticipated use during the study
- use of contact lenses in either eye within 1 month prior to the screening visit (week -2), or anticipated contact lens wear in either eye during the study
- [Redacted]

Approval Date: 19-Jan-2017

Stage 2:

- participation in stage 1 of this study

Response Measures

Stage 1:

Safety:

- adverse events
- best-corrected visual acuity (BCVA; manifest refraction at screening and exit visits)
- macroscopic hyperemia assessment and slit-lamp biomicroscopy
- dilated ophthalmic exam
- photographic conjunctival hyperemia assessment
- intraocular pressure (IOP)
- vital signs
- laboratory tests (chemistry, hematology, urinalysis)
- urine pregnancy test (for females of childbearing potential)

Pharmacokinetics:

- ocular pharmacokinetics (assessed from tear samples)
- systemic pharmacokinetics

[REDACTED]

- [REDACTED]
- [REDACTED]
- [REDACTED]
- [REDACTED]
- [REDACTED]
- [REDACTED]
- [REDACTED]

Health Outcomes:

- Supplemental Dry Eye Patient Reported Outcomes Questionnaire

[REDACTED]

- [REDACTED]
- [REDACTED]

Approval Date: 19-Jan-2017

| [REDACTED]
| [REDACTED]
| [REDACTED]
| [REDACTED]
| [REDACTED]
| [REDACTED]
| [REDACTED]

[REDACTED]

| [REDACTED]
| [REDACTED]

[REDACTED]

| [REDACTED]
| [REDACTED]
| [REDACTED]
| [REDACTED]
| [REDACTED]
| [REDACTED]
| [REDACTED]
| [REDACTED]
| [REDACTED]
| [REDACTED]

[REDACTED]

| [REDACTED]
| [REDACTED]

General Statistical Methods and Types of Analyses:

[figure not shown]
For both stages 1 and 2, the safety population, consisting of all patients who receive study treatment, will be used for safety analyses. The modified intent-to-treat (mITT) population, consisting of all patients who receive study treatment and have baseline and at least 1 postbaseline assessment for 1 or more of the exploratory efficacy measurements, will be used for exploratory efficacy analyses. In general, continuous variables will be summarized by descriptive statistics including sample size (N), mean, standard deviation, median, minimum, and maximum. Categorical variables will be summarized by frequency count and percentage.

[figure not shown]
Exploratory efficacy (stage 1 and stage 2) measures will be evaluated. Baseline and change from baseline measure will be assessed. Also, number (percent) of responders may be assessed.

For both stages 1 and 2, a model-independent approach will be used to calculate pharmacokinetic parameters of CsA, if appropriate, for tears and blood. Pharmacokinetic parameters for blood and tears will only be calculated for samples collected from patients who receive study treatment.

[figure not shown]
The Medical Dictionary for Regulatory Activities (MedDRA) nomenclature will be used to code adverse events. The number and percentage of patients with treatment-emergent adverse events will be tabulated based on the primary system organ class and the preferred term using the safety population. The adverse events will be classified as ocular versus nonocular adverse events and analyzed separately.

Sample Size Calculation: The sample sizes for stages 1 and 2 were determined empirically.

Approval Date: 19-Jan-2017

Approval Date: 19-Jan-2017

[figure not shown]

Approval Date: 19-Jan-2017

Treatment and Response Measurements by the Investigators

This study requires a follow-up investigator and a treating investigator. Certain study tests and procedures are assigned to the treating investigator to maintain masking of the follow-up investigator to the study treatments. The treating investigator will conduct RESTASIS X administration, macroscopic regional hyperemia, slit lamp biomicroscopy (eyelids, margins, lashes, and conjunctiva), all dilated ophthalmic examinations, and impression cytology for biomarker analysis. [REDACTED]

[REDACTED]. The follow-up investigator or appropriately trained and qualified site personnel will administer all other procedures. See Table 5 for a listing of investigator's procedure assignments.

Approval Date: 19-Jan-2017

1 Background and Clinical Rationale

This study represents the first evaluation in patients of the safety, exploratory efficacy, and pharmacokinetics of RESTASIS® X, [REDACTED] cyclosporine (CsA). The study will be conducted in patients with moderate to severe dry eye disease.

[REDACTED]

[REDACTED] (CFI) is a new formulation of CsA [REDACTED]. To fully evaluate F1, F2, and CFI, this phase 2 study will be conducted in 2 stages.

1.1 Study Rationale

Cyclosporine, a cyclic peptide containing 11 amino acids with a total molecular weight of 1202 Daltons, has long been known as a potent immunosuppressant and anti-inflammatory agent that specifically inhibits T lymphocyte proliferation via inhibition of Interleukin-2 (IL-2) expression and cytokine production (Nussenblatt and Palestine, 1986; Petcher et al, 1976). At the molecular level, CsA functions by binding to and forming a complex with cytosolic Cyclophilin A. The CsA:Cyclophilin A complex in turn inhibits the calcium/calmodulin-dependent phosphatase activity of calcineurin that is responsible for dephosphorylation and translocation of nuclear factor of activated T cells (NFATc), a transcription factor required for IL-2 gene expression and T-cell activation (Ho et al, 1996). In addition to NFATc inhibition, CsA negatively regulates inflammation through its ability to bind and inhibit the phosphorylation of Inhibitor of κ B (I κ B), thereby preventing nuclear translocation of NF- κ B, a key transcription factor for multiple proinflammatory cytokine/chemokine genes. Additional molecular mechanisms reported to be inhibited by CsA include c-fos/jun and AP-1 transcription factors, and key inflammation-related intracellular signaling pathways including p38 mitogen-activated protein kinase, c-Jun N-terminal kinase, and extracellular signal-related kinase.

In ophthalmology, prior to its use as a topical treatment for dry eye disease, systemic (intravenous and oral) CsA was used for the treatment of severe posterior segment inflammation (Masuda et al, 1989). Ulcerative keratitis associated with Wegener's

granulomatosis, severe Grave’s ophthalmopathy, and graft rejection after keratoplasty have also been successfully treated with systemic CsA (Georganas et al, 1996; Nussenblatt et al, 1991; Prummel et al, 1989; Reinhard et al, 1997). It was found, however, that systemic administration could be accompanied by side effects such as nephrotoxicity and hypertension (Mihatsch et al, 1998). To increase local drug concentrations and avoid systemic side effects, topical ophthalmic CsA was developed. Topical ophthalmic CsA is marketed by Allergan in over 25 countries as RESTASIS (cyclosporine ophthalmic emulsion 0.05%) for increasing tear production in patients whose tear production is presumed to be suppressed due to ocular inflammation associated with keratoconjunctivitis sicca.

Supporting CsA’s mechanism of action as an inhibitor of T-cell activation and its applicability for treatment of dry eye disease, Kunert and colleagues (2000) evaluated conjunctival biopsy specimens from 32 patients with dry eye disease: 13 treated with 0.05% CsA, 6 with 0.1% CsA, and 13 with vehicle alone for 6 months. Conjunctival biopsies from patients given topical CsA showed relative decreases in the numbers of cells positive for CD3, CD4, and CD8. In addition, biopsies from patients treated with 0.05% topical CsA showed a significant decrease in the number of cells expressing the inflammatory markers CD11a and human leukocyte antigen type DR (HLA-DR). A reduction in the expression of markers of general inflammation such as CD11a and HLA-DR, suggests that perhaps through its direct inhibitory effect on activated T cells, CsA indirectly reduces the overall magnitude of inflammation, thus contributing to a more quiescent status in the tissue.

In nonclinical studies in rabbits and dogs, [REDACTED]
[REDACTED]
[REDACTED]
[REDACTED]
[REDACTED]
[REDACTED]
[REDACTED]
[REDACTED] To
date, no studies have been completed with RESTASIS X in humans, so its safety, pharmacokinetics, and pharmacology have yet to be determined. In the study described here, RESTASIS X will be evaluated in patients who were previously diagnosed with moderate to severe dry eye disease but have not been treated with topical RESTASIS for at least 3 months prior to entering the study. [REDACTED]
[REDACTED]
[REDACTED]

Approval Date: 19-Jan-2017

[REDACTED]

[REDACTED]

2 Study Objectives and Clinical Hypotheses

2.1 Study Objectives

The study will be conducted in 2 stages:

Stage 1:

To evaluate the safety, exploratory efficacy, and pharmacokinetics of F1 and F2 administered [REDACTED] in patients with moderate to severe dry eye disease.

Stage 2:

To evaluate the safety, exploratory efficacy, and pharmacokinetics of CFI administered [REDACTED] in patients with moderate to severe dry eye disease.

2.2 Clinical Hypotheses

[REDACTED]

[REDACTED]

[REDACTED]

significant safety findings [REDACTED], the remaining 2 patients in cohort 2 will be given a [REDACTED] vehicle in one eye and [REDACTED] F1 [REDACTED] in the other eye. After 2 weeks of monitoring, and in the absence of significant safety findings [REDACTED], four patients in cohort 3 will receive [REDACTED] vehicle in one eye and [REDACTED] F1 [REDACTED] in the other eye. After 2 weeks of monitoring the fourth patient in cohort 3, [REDACTED]

[REDACTED]
[REDACTED]
[REDACTED]
[REDACTED]
[REDACTED]

Four patients in cohort 4 will receive [REDACTED] of vehicle in one eye and [REDACTED] F1 [REDACTED] in the other eye. Two weeks after dosing the fourth patient in cohort 4, [REDACTED]

[REDACTED]
[REDACTED]

In the absence of significant safety findings from the first 4 patients in cohort 4, cohorts 5A and 6A will begin. For cohort 5A, patients will be administered [REDACTED] F1 [REDACTED] in one eye and [REDACTED] vehicle in the other eye. After 2 weeks of monitoring the first 4 patients in cohort 5A, [REDACTED]

[REDACTED] If there are no significant safety findings for the first 4 patients in cohort 5A, the dosing of the remaining 4 patients in cohort 5A will proceed, and then the first 4 patients of cohort 5B will be administered [REDACTED] of F1 [REDACTED] in one eye and [REDACTED] vehicle in the other eye.

For cohorts 6A and 6B, patients will receive [REDACTED] either F2 or vehicle (see Figure 1 and Table 1). For cohorts 6C and 6D, patients will receive [REDACTED] of either F1 or F2 and vehicle (see Figure 1 and Table 1). The doses [REDACTED] associated with cohorts 6A, 6B, 6C, and 6D will be determined [REDACTED] The progression from cohort 6A to 6B will be conducted in the same manner as for cohorts 3 through 5, with decisions to continue with dosing of a given cohort and/or to escalate to the next higher dose cohort based upon [REDACTED]

[REDACTED]
[REDACTED]
[REDACTED]

Approval Date: 19-Jan-2017

[Redacted text block]

[Redacted text block]

[Redacted text block]

[Redacted text block]

[Redacted text block]

[Redacted text block]

[Redacted text block]

[Redacted text block]

Approval Date: 19-Jan-2017

[REDACTED]

4 Study Population and Entry Criteria

4.1 Number of Patients

The study anticipates enrolling up to 87 patients.

Stage 1: Stage 1 will be conducted at approximately 10 sites and will have up to 63 patients and approximately 10 cohorts (cohorts 1 to 6D). The anticipated number of patients per cohort are 3 for cohort 1; 4 each for cohorts 2, 6C, and 6D; and 8 each for cohorts 3 through 6B.

Stage 2: Stage 2 will be conducted at approximately 15 sites and will have up to 24 patients and 3 treatment groups. The number of treatment groups and number of patients per group will be based on results from stage 1.

4.2 Study Population Characteristics

Stage 1: patients with moderate to severe dry eye disease

[REDACTED]

4.3 Inclusion Criteria

The following are requirements for entry into the study:

General Inclusion Criteria for Both Stages 1 and 2

1. male or female, at least 18 years of age at screening visit (week -2)
2. at baseline (day 1) visit, dry eye disease (keratoconjunctivitis sicca) in both eyes, characterized by the following clinical signs:

[Redacted text]

3. [Redacted text]
4. best-corrected visual acuity (BCVA) of 20/100 or better (Snellen equivalent), using the logarithm of the minimum angle of resolution (LogMAR) in each eye at the screening (week -2) and baseline (day 1) visits

[Redacted text]

4.4 Exclusion Criteria

The following are criteria for exclusion from participating in the study:

For Stages 1 and 2:

1. use of topical RESTASIS or any other topical ophthalmic preparation of CsA within 3 months prior to the baseline visit (day 1) and unwilling/unable to discontinue use for 3 months prior to baseline, or anticipated use during the study
2. any use of systemic or dermatologic CsA or other calcineurin inhibitors within 3 months prior to the screening visit (week -2), or anticipated use during study

[Redacted text block containing multiple paragraphs of blacked-out content]

Approval Date: 19-Jan-2017

[Redacted text block]

- [Redacted list item]

- [Redacted list item]

[Redacted text block]

- [Redacted list item]

- [Redacted list item]

- [Redacted list item]

- [Redacted list item]

- [Redacted list item]

- [Redacted list item]

[Redacted text block]

Approval Date: 19-Jan-2017

[REDACTED]

[REDACTED]

[REDACTED]

Stage 2:

35. participation in stage 1 of this study

4.5 Permissible and Prohibited Medications/Treatments

4.5.1 Permissible Medications/Treatments

Allergan will provide patients with REFRESH PLUS, the only topical artificial tear permitted during the study. Patients will be required to replace any existing artificial tear product with REFRESH PLUS.

During the 2-week period between the screening and baseline visits, REFRESH PLUS should be instilled in both eyes 4 times per day.

Following the baseline visit, REFRESH PLUS can be used up to 4 times per day. Use of REFRESH PLUS should not occur within 6 hours prior to any study visit.

Use of inhaled corticosteroids (as needed) is permitted during the study.

Use of the following systemic medications and supplements is permitted during the study, providing a stable dosing regimen is established (dosing is not stable if a patient starts, stops, or changes dose/drug during the study):

- cholinergic agonists or antihistamines, antimuscarinics, diuretics, tricyclic antidepressants, phenothiazines, cholesterol lowering agents
- systemic vitamins and/or systemic supplements containing omega 3 fatty acids; vitamins A, B, and E; fish oil; or Evening Primrose oil
- hormone replacement therapy program, oral or transdermal contraception use, use of other estrogen or progesterone treatment
- systemic androgen replacement therapy
- systemic inhibitors of steroidogenesis, spironolactone, cyproterone acetate, or other anti-androgen treatment

- oral macrolides, tetracyclines, tetracycline derivative drugs (including doxycycline and minocycline)
- non-ophthalmic retinoids (eg, isotretinoin), non-ophthalmic corticosteroids, or other non-ophthalmic anti-inflammatory medications or immune modulators used for prolonged treatment of systemic immune-mediated diseases

4.5.1.1 Definition of Females of (Non-)Childbearing Potential and/or Acceptable Contraceptive Methods

Women who are not of childbearing potential are either postmenopausal (and with at least 12 consecutive months without menstruation) or permanently sterilized (eg, tubal occlusion, hysterectomy, bilateral salpingectomy).

Natural menopause is defined as the permanent cessation of menstrual periods, determined retrospectively after a woman has experienced 12 months of amenorrhea without any other obvious pathological or physiological cause. For women of childbearing potential who may participate in the study, the following methods of contraception, if properly used, are generally considered reliable: oral contraceptives, patch contraceptives, injection contraceptives, male condom with intravaginal spermicide, diaphragm or cervical cap with spermicide, vaginal contraceptive ring, intrauterine device, surgical sterilization (bilateral tubal ligation), vasectomized partner, or sexual abstinence.

The investigator and each patient will determine the appropriate method of contraception for the patient during their participation in the study.

If a female becomes pregnant during the study, the investigator will notify Allergan immediately after the pregnancy is confirmed and the patient will be exited from the study after appropriate safety follow-up. The investigator will (1) notify the patient's physician that the patient was being treated with an investigational drug (RESTASIS X/CsA), and (2) follow the progress of the pregnancy. The investigator must document the outcome of the pregnancy and provide a copy of the documentation to Allergan.

4.5.2 Prohibited Medications/Treatments

The decision to administer a prohibited medication/treatment is done with the safety of the study participant as the primary consideration. When possible, Allergan should be notified before the prohibited medication/treatment is administered.

The following medications or classes of medications are prohibited during the study:

- any systemic/dermatological/ophthalmic use of RESTASIS/CsA or other calcineurin inhibitors
- any artificial tear product other than REFRESH PLUS
- use of REFRESH PLUS greater than 4 times per day or within 6 hours prior to a study visit
- use of any topical ocular medication other than REFRESH PLUS
- use of Lacrisert™ (hydroxypropyl cellulose ophthalmic insert) or methylcellulose ocular inserts

The following procedures/treatments are prohibited during the study:

- insertion of punctal plugs
- punctal cautery in either eye
- use of contact lenses in either eye
- use of scleral lenses, or sealed compartment ocular frames
- LipiFlow or other lid-heating therapy, meibomian gland probing or therapeutic gland expression in either eye
- anterior segment surgery or trauma that could affect corneal sensitivity (eg, cataract surgery or any surgery involving a limbal or corneal incision) in either eye
- insertion or removal of glaucoma filtration shunts or devices

4.5.3 Rescue Medications

In the event that rescue medication is required for worsening signs or symptoms of dry eye disease during the course of the study, patients will be provided an appropriate rescue regimen by the investigator/treating clinician, and be monitored through the end of the study.

5 Study Treatments

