8.9 Withdrawal Criteria

The investigator and Allergan have the right to withdraw a patient from the study at any time for any reason. When possible, the decision to withdraw a patient from study treatment or the study should be discussed with Allergan.

Patients should be discontinued from the study if any of the following criteria are met:

- patient develops (or has an exacerbation of) any medical condition that, in the opinion of the investigator, would put the patient at an unacceptable medical risk or compromises the patient's ability to participate in the study
- patient is unwilling or unable to continue to comply with study procedures

Patients who are withdrawn early from the study during a study visit should have the exit procedures completed when possible.

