5.1.1 Statistical and Analytical Plans

5.1.1.1 Common Conventions

5.1.1.1.1 Analysis Populations

The analysis populations will consist of patients as defined in [Table 5-1](#).

Table 5-1 Analysis Populations – Stage 1

Population	Definition	Study Treatment
Safety	All patients who are treated	Actual received ^a
Modified intent-to-treat (mITT)	All randomized patients who have baseline and at least 1 postbaseline assessment for 1 or more of the exploratory efficacy measurements	Randomized assignment

^a Patients will be summarized according to the first study treatment received or study treatment received for majority of treatment period.

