5.1.1.1.3 Statistical Methodology

The methodologies defined in Table 5-2 apply as specified to individual endpoints defined in this SAP for stage 1.

Table 5-2 Statistical Methodology – Stage 1

Methodology	Description
Categorical counts	
 • Number of patients in individual categories 
 ○ Patients with ≥ 1 qualifying event counted once per individual category
Categorical descriptives	
 • Number and percentage of patients in individual categories 
 ○ Patients with ≥ 1 qualifying event counted once per individual category • N1 if percentage denominator \neq number of patients in the population (standard percentage denominator) 
 ○ N1 = patients with nonmissing value
Continuous descriptives	
 • N1, mean, SD, median, minimum, maximum • N1 = patients with nonmissing value
CFB descriptives	
 • Continuous descriptives for baseline, postbaseline, and CFB values • N1 = patients with nonmissing values at both baseline and the specified postbaseline analysis visit
Responder	
 • Categorical descriptives for responders and nonresponders • N1 = patients with nonmissing values at both baseline and the specified postbaseline analysis visit

CFB = change from baseline

Two treatment cycles are defined in this analysis plan. Treatment Cycle 1 includes all visits from study baseline (also called cycle 1 baseline) to Week 24 or Exit visit if a patient receives ██████████ throughout the study, or to the last visit before retreatment if a patient receives ██████████ during the study. For visits in treatment Cycle 1, refer to study windows in Section 6.2. Treatment Cycle 2 applies to patients who receive retreatment, and includes all visits from retreatment and thereafter. Visits in treatment Cycle 2 will be determined based on the study days relative to the retreatment visit using the study windows specified in Section 6.2.

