5.1.1.1.4 Missing Data

General missing data handling conventions are summarized as follows:

- Missing data will not be imputed and all analyses will be based on observed data.
- Partial dates handling conventions are specified in Section 6.3, but will be listed in the data listings as they appear on the electronic case report forms (eCRFs).

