5.1.1.3.6 Ocular Surface Disease Index

The Ocular Surface Disease Index (OSDI) Questionnaire consists of 12 questions based on which the total score (questions 1-12) and 3 subscales including ocular symptoms (questions 1-3), vision-related functioning (questions 4-9), and environmental triggers (questions 10-12) will be computed. The patients will be asked to rate each symptom using a 5-point scale (0 to 4), where 0 = none of the time, 1 = some of the time, 2 = half of the time, 3 = most of the time, and 4 = all of the time. Seven questions allow a response of not applicable (N/A). A higher score represents greater disability.

The OSDI Questionnaire scores will be summarized by treatment group as shown in [Table 5-14](#).

Table 5-14 Ocular Surface Disease Index Summaries

Endpoint	Description	Timing	Methodology
OSDI score ^a	Summary by analysis visit and by 
 The total OSDI score The 3 subscale scores (specified in Table 6-20) 	Cycle 1: Study baseline (Day 1) and Weeks 4, 12, and 24 Cycle 2: Cycle baseline and Weeks 4R and Week 12R	CFB descriptives
Number (percent) of responders	Summary by analysis visit 
 Responder is defined as ≥ 20 point decrease from study baseline in total OSDI score 	Cycle 1: Weeks 4, 12, and 24	Categorical descriptives

^a All ocular surface disease index data will be listed.

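### In the visible stage 1 SAP, values recorded after dry-eye rescue feed the Schirmer and OSDI responder counts and the change summaries, so a rescued patient can be tabulated as a responder

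*Protocol*

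**What the plan says.** **Rescue and follow-up.** Protocol 4.5.3 sets the trigger: "In the event that rescue medication is required for worsening signs or symptoms of dry eye disease during the course of the study". It then says that "patients will be provided an appropriate rescue regimen by the investigator/treating clinician, and be monitored through the end of the study". Protocol 8.9 introduces its withdrawal list with "Patients should be discontinued from the study if any of the following criteria are met". The two criteria that follow are medical risk or compromised participation, and unwillingness or inability to comply. Rescue is not one of them.

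**Data used.** SAP 5.1.1.1.4 states: "Missing data will not be imputed and all analyses will be based on observed data". The SAP's mITT definition (Table 5-1) is "All randomized patients who have baseline and at least 1 postbaseline assessment for 1 or more of the exploratory efficacy measurements". It has no condition on rescue or prohibited medication.

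**Responder definitions.** In Table 5-14, "Responder is defined as ≥ 20 point decrease from study baseline in total OSDI score", reported at Cycle 1 Weeks 4, 12 and 24. Table 5-9 defines a Schirmer responder by a rise of at least 10 mm/5 min from study baseline, at Cycle 1 Weeks 4, 8, 12 and 24. For responder and change summaries, Table 5-2 gives the denominator as "N1 = patients with nonmissing values at both baseline and the specified postbaseline analysis visit".

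**Where rescue could show.** No visible SAP section names rescue. A rescue drug could appear in the general concomitant medication summary (Table 5-8). If it is a topical ocular product, which Protocol 4.5.2 otherwise prohibits, it could also be a protocol deviation (Table 5-5).

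**The concern.** Rescue is given because the disease has worsened. If it works, later Schirmer or OSDI values reflect the rescue regimen as well as the study treatment. A responder rule that looks only at change from study baseline cannot tell the two apart, and may record as a success a patient whose course on study treatment was a worsening. The change-from-baseline summaries, including those for staining and for Cycle 2, take in post-rescue values in the same way.

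What is at stake is how a small descriptive table is read. Cohorts have 3 to 8 patients, so a single misclassified patient is visible in the rate. Protocol 7.6 and SAP 5.1.1.7 say that analyses after the interim lock are to support the design of future studies.

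**Working it through.** **1. The plan's own count.** SAP 5.1.2 anticipates 3 patients in Cohort 1, 4 in each of three cohorts (2, 6C, 6D) and 8 in each of six (3, 4, 5A, 5B, 6A, 6B):

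3 + 3 × 4 + 6 × 8 = 63, which matches the stated maximum for stage 1.

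The sample size is empirical, so there is no power figure to reproduce.

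**2. The path from rescue to responder.**
- The patient is rescued and remains in the study (Protocol 4.5.3, 8.9), so later visits can yield efficacy values.
- Those values are observed, and no visible rule sets them aside (SAP 5.1.1.1.4).
- The patient stays in mITT (Table 5-1).
- The visit-window conventions in SAP 6.2 select by scheduled status and closeness to the target day, without regard to rescue.
- Responder status needs only the cut-off. Tables 5-9 and 5-14 name categorical descriptives as the method, and Table 5-2 also has a responder row. Under either, the value need only be nonmissing.

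For example, a patient rescued at Week 6 who meets a cut-off at Week 12 is tabulated as a Week 12 responder.

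**3. Effect of one such patient.** Step in the rate = 100/n, if all n are evaluable:

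| Cohort size n | Step (percentage points) |
|---|---|
| 8 | 100/8 = 12.5 |
| 4 | 100/4 = 25.0 |
| 3 (Cohort 1, vehicle and sham) | 100/3 = 33.3 |

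**4. How many patients.** The documents give neither a rescue rate nor a response rate after rescue. Assume a share r = 5 to 20% rescued, of whom q = 25 to 50% meet a cut-off.

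- Expected overstatement of a rate = r × q: 0.05 × 0.25 = 1.25 points, up to 0.20 × 0.50 = 10 points.
- Expected misclassified patients = 63 × r × q: 63 × 0.0125 = 0.8, up to 63 × 0.10 = 6.3, so about 1 to 6.
- Chance of at least one = 1 − (1 − r × q)^n:

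| n | r × q = 1.25% | r × q = 10% |
|---|---|---|
| 8 | 9.6% | 57.0% |
| 4 | 4.9% | 34.4% |
| 63 | 54.7% | 99.9% |

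These ranges show scale only; none of the inputs r and q comes from the documents.

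**The case against.** **The rule may exist out of sight.** Protocol 6.3 and 7.3.2 and SAP 6.4 are redacted, and deviation definitions and table specifications are in separate documents. This stands as a limit. The SAP's table list shows only VAS and OSDI scoring tables (6-18 to 6-20) at the redacted place, and the visible responder rows carry no exception, but a hidden rule cannot be ruled out.

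**The observed-data sentence is about missing data.** It sits under that heading and does not address rescue, so the plan is silent rather than deciding that rescue should count as success. That is fair. The result of following the visible text is the same.

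**Using all observed data is a legitimate treatment-policy choice.** It is, and neither document says that rescue means failure. However, the plan does not state that choice either, and it gives the reader no rescue table by which to interpret the rates.

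**Monitoring may mean safety only.** Protocol 4.5.3 does not say so and does not stop efficacy assessments.

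**A rescued patient can be traced by hand.** Schirmer and OSDI data are listed, medications are summarised and significant deviations are listed. With 3 to 8 patients per cohort this helps, but it does not correct the tabulated rate.

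**Stronger readings that the documents do not support.**
- A reader might infer that the plan credits post-rescue improvement to the drug, or that rescue of a vehicle eye shrinks a planned between-eye difference. The visible SAP tabulates by cohort and summarises study and contralateral eyes separately (5.1.1.1.3), with no between-eye estimate or test. OSDI is a patient-level score with no eye contrast.
- Staining has no responder definition (5.1.1.3.3, 5.1.1.3.4), so only its change summaries are touched.
- Taking 5 to 20% of 63 gives 3 to 13 patients, but that counts everyone rescued at an assumed rate, not false responders.

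**Conclusion.** The point holds for stage 1 on the visible text. Schirmer and OSDI responder status in Cycle 1, and the change-from-baseline summaries in both cycles, take in values recorded after rescue, and a patient rescued for worsening dry eye can be counted as a responder. This goes beyond a missing detail, because the visible rule gives a misleading count when it is followed.

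The size is one step of 12.5 or 25 points per patient in cohorts of 8 or 4. The estimate of about 1 to 6 misclassified patients out of 63 rests wholly on the assumed rescue and response shares. The consequence is a distorted descriptive rate for an exploratory endpoint. It is not a matter of type I error, power or a formal treatment comparison. The stage 2 SAP is a separate document that was not available, so nothing is concluded about it. This is a worthwhile, low-cost improvement and not a serious flaw.

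**What to change.** - **Responder rows.** In Tables 5-9 and 5-14, count the eye (Schirmer) or the patient (OSDI) as a nonresponder at visits on or after the first rescue, and keep it in N1.
- **Laterality.** If the rescued eye is not recorded, flag both eyes.
- **Dates.** Do not let SAP 6.3.2 place a rescue before treatment. Its target is the day before treatment start. Under Table 6-17, a fully missing start date goes to that target, as does one in the same year with no month or in the same month with no day. Rescue dates need their own rule or a query to the site.
- **Capture.** Identify rescue with an explicit flag. The general medication data may not mark it, and a non-drug regimen might not appear there.
- **Change tables.** Keep the observed-data versions and add a supplementary set without post-rescue values.
- **Rescue use.** Tabulate it by cohort and eye.

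The clinical rescue provision in Protocol 4.5.3 is left unchanged. The cost is a rescue flag with usable dates and one extra run. Responder rates may come out slightly lower.
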